To achieve the primary aim, MR elastography will be performed in up to 104 healthy children, somewhat evenly divided (approximately 48 each) into two age groups (7-<12years, 12-<18years). Means, standard deviations and 95% confidence intervals for normal liver stiffness will be calculated for each age group and values will be compared across groups.

Multi-site secondary aims and hypotheses are as follows:

- To assess cross-platform variability in normal MRI liver stiffness values. We hypothesize that there will be no significant difference in mean normal liver stiffness values obtained on three different vendor platforms (GE, Philips, Siemens).
- 2. To assess for cross-field strength variability in normal MRI liver stiffness values. We hypothesize that there will be no significant difference in mean normal liver stiffness values obtained at 1.5T versus 3T.
- 3. To assess for sex-related (male vs. female) differences in normal MRI liver stiffness values. We hypothesize that there will be no sex-related differences in normal liver stiffness measured by MR elastography.

To achieve secondary aim #1, subject recruitment will be stratified across sites with approximately 32 subjects in each age group being imaged on each of the different vendor platforms (GE, Philips, Siemens). To achieve secondary aim #2, subject recruitment will be stratified across 1.5T and 3T magnets with approximately 48 subjects in each age group being imaged at each of the different field strengths. To achieve secondary aim #3, approximately equal numbers of male and female subjects will be recruited in each of the two age groups.

CCHMC exploratory aims and hypotheses are as follows:

1. To determine normal corrected T1 (cT1) values for two pediatric age groups. We hypothesize that there will be no significant difference in mean cT1 values between age groups or between field strengths.

Overall research strategy:

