We propose to conduct a multi-institutional study of normal liver stiffness values in pediatric subjects with no known history of liver disease. The requirement for multiple sites relates to the need to acquire normative stiffness values on each of the three major MRI vendor platforms to assess for unexpected cross-platform variability in liver stiffness. CCHMC has Philips MRI scanners (1.5 and 3T) equipped with MR elastography but does not have access to GE or Siemens MRI scanners in a research environment. Massachusetts General Hospital (MGH) has an elastography capable GE scanner (1.5T), Children's Hospital of Philadelphia (CHOP) has elastography-capable GE and Siemens scanners (3T), and Mallinckrodt Institute of Radiology (MIR) has an

elastography-capable Siemens scanner (1.5T). This human study protocol will be submitted for approval to the Institutional Review Board at CCHMC. CCHMC will serve as the lead site. CHOP, MGH and MIR may choose to submit to their IRB or to rely on the CCHMC IRB.

Power calculation relevant to SA1: Determine normal liver stiffness values (and associated normal ranges) as measured by MR elastography for three pediatric age groups: Based on the standard deviation of normal liver stiffness measurements in the study by Etchell et al. (SD=0.3 kPa) and the confidence intervals from a study of healthy adult livers by Lee et al. (95% CI ~±0.1 kPa), we calculate that a sample size of n=18 is needed in each group to achieve 2-sided 95% confidence intervals with a distance from the mean to the limits that is equal to 0.15 kPa for each group [Etchell, Lee]. This sample size also provides 80% power to detect an effect size (Cohen's d) of 0.67 between the two age groups. Given the prior study findings of a correlation between subject age and liver stiffness, we will recruit into two subject age groups (7-<12years, 12-<18 years). Based on prior published and unpublished MRI studies of "healthy volunteers" at CCHMC, we expect up to 25% of "healthy subjects" recruited for this study will have unsuspected liver disease manifest as abnormalities in liver function tests or liver fat fraction values greater than 5% by MRI proton density fat fraction (PDFF) (12). Therefore, we will increase recruitment targets by 25% over the levels required to achieve adequate statistical power. Thus, approximately 24 subjects will be recruited to each group at each field strength for a total study recruitment of n= up to 104.

MR imaging:

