All imaging will be performed using multi-channel phased-array torso coil. MR elastography will be performed utilizing the manufacturer product MRE sequence (generally 2D gradient recalled echo at 1.5T and 2D spin echo echo-planar imaging at 3T) and the manufacturer standard 60 Hz frequency. For the GRE sequence, driver amplitude will be adjusted based on patient weight (no adjustment required for SE-EPI). Per standard protocol, four axial slices will be acquired through the bulk of the central liver. PDFF sequences will be performed per manufacturer recommended settings. Total imaging time will be less than 15 minutes per examination and will be accomplished with approximately six breath holds.

Sequences acquired will include:

- 1. 3-plane localizer
- 2. MR elastography (manufacturer recommended)
- 3. PDFF sequence
- 4. Axial T2-weighted single-shot fast spin-echo (anatomic sequence)

Driver amplitude will be adjusted as follows for the GRE sequence: GRE:

Patient weight	Amplitude
40-49 kg	40%
50-59 kg	50%

60-69 kg	60%
70-79 kg	70%
80-89 kg	80%
90-99 kg	90%
100+ kg	100%

Additional sequences will be acquired at CCHMC only. These will extend the total imaging time to up to 30 minutes and additional breath holds.

Corrected T1

MR exam post-processing:

All PDFF and MR elastography images will be processed both locally and centrally at a single site (CCHMC) by a single trained observer to ensure uniformity in post-processing technique. Post-processing will be performed as previously described with placement of single large regions of interest in the right hepatic lobe (12). Central MR elastography data will be post-processed using MRE Lab (Mayo Clinic, Rochester, MN) and PDFF data will be post-processed using Philips Intellispace (Philips Healthcare, Best, The Netherlands).

De-identified cT1 data acquired at CCHMC only will be sent to Perspectum Diagnostics for analysis.

5. DURATION:

18 months: 1 year for subject accrual, 6 months for analysis and write-up

6. SELECTION & RECRUITMENT OF PARTICIPANTS:

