Healthy pediatric subjects without a known history of liver disease will be recruited via advertising through established hospital channels (e.g. email) and posted flyers and/or posters at each of the study sites. Based on prior studies of normal subjects at CCHMC, we anticipate no difficulty recruiting the required number of subjects for this study. For a prior study of pancreatic function in normal subjects that required MRI and placement of an intravenous catheter, 142 responses expressing interest in participating in the study were received within 4 days of study announcement.

For each age group, MRI vendor and field strength, approximately half the recruited subjects will be male and half will be female. CCHMC will recruit a total of 32 subjects (16 male, 16 female), CHOP will recruit up to 40 subjects (approximately 20 male, 20 female), and MIR and MGH will each recruit a total of 16 subjects (8 male, 8 female).

Inclusion criteria:

- 1. Age 7-less than 18 years of age
- No documented history of liver disease
- 3. English speaking*

Exclusion criteria:

1. NPO less than 4 hours

- 2. Body mass index < 10th or > 85th percentile for age
- 3. Documented history of liver disease
- 4. Pregnancy
- 5. Inability to lie still for duration of the MRI
- 6. Inability to breath hold for the duration of the 15-20 second MR elastography sequence
- 7. Standard contraindication to MRI (implanted hardware, etc.)
- 8. Requirement of sedation or general anesthesia for MRI
- 9. Abnormality of any prior measured liver function test**
- 10. Any prior liver fat fraction > 5% by MRI PDFF**

*English speaking has been included as an inclusion criterion as successful performance of an MRE examination requires following detailed and repeated breath hold instructions. This is a multicenter study and interpreter services are not uniformly available in the imaging research environment across participating institutions.

**Research results meeting this exclusion will eliminate subjects from population analysis

7. PROCESS OF OBTAINING CONSENT:

Participants will be screened in advance of enrollment by study personnel to determine baseline eligibility for participation. Once eligibility has been confirmed, written informed consent will be obtained in person at the time of the research visit.

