All PDFF and MR elastography images will be processed both locally and centrally at a single site (CCHMC) by a single trained observer to ensure uniformity in post-processing technique. Post-processing will be performed as previously described with placement of single large regions of interest in the right hepatic lobe (12). Central MR elastography data will be post-processed using MRE Lab (Mayo Clinic, Rochester, MN) and PDFF data will be post-processed using Philips Intellispace (Philips Healthcare, Best, The Netherlands).

De-identified cT1 data acquired at CCHMC only will be sent to Perspectum Diagnostics for analysis.

Descriptive statistics will be utilized to describe the characteristics of each subject group (age, sex, scanner manufacturer, field strength). Normal liver stiffness for each age group will be summarized as mean ± std with range and 95% confidence interval also provided. Two sample t-test or one-way analysis of variance (ANOVA) will be used to assess for differences in liver stiffness between age groups and between different groups of categorical variables (sex, scanner manufacturer, field strength). The correlation between liver stiffness and continuous variables will be assessed by using Pearson on Spearman correlation coefficients as appropriate. Multiple linear regression models will be utilized to evaluate the association between liver stiffness and the predictor variables adjusting for all other covariates. Box plots will be generated to visually illustrate the results from the group comparisons mentioned above. All analyses will be performed using SAS version 9.4. A p-value less than 0.05 will be considered statistically significant for all inference testing.

10. FACILITIES and PERFORMANCE SITES:

Research blood draws will occur in the Schubert Research Clinic. All other study procedures will occur in the CCHMC Imaging Research Center (IRC).

11. POTENTIAL BENEFITS:

There are no direct benefits to study participants. This research, however, is critical for our understanding of normal MRE values in children which are relevant to the diagnosis of disease utilizing MRE. Therefore this research has potential future benefit to children with known or suspected liver disease.

12. POTENTIAL RISKS, DISCOMFORTS, INCONVENIENCES AND PRECAUTIONS:

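### Secondary aim 2 cannot separate field strength from pulse sequence, and its pooled test carries a CHOP effect; Philips versus the other vendors is the same contrast as CCHMC versus the other sites

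*Combined protocol and SAP*

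**What the plan says.** Secondary aim 2 (Section 4) is "To assess for cross-field strength variability in normal MRI liver stiffness values", with a hypothesis of no difference between 1.5T and 3T. Secondary aim 1 makes the same kind of claim for the GE, Philips and Siemens platforms.

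Under MR imaging, the sequence is "generally 2D gradient recalled echo at 1.5T and 2D spin echo echo-planar imaging at 3T". The driver setting also differs: "For the GRE sequence, driver amplitude will be adjusted based on patient weight (no adjustment required for SE-EPI").

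The overall research strategy in Section 4 lists the equipment. "CCHMC has Philips MRI scanners (1.5 and 3T) equipped with MR elastography but does not have access to GE or Siemens MRI scanners" for research. MGH has GE at 1.5T, MIR has Siemens at 1.5T, and CHOP has GE and Siemens at 3T. Section 6 has CCHMC recruiting 32 subjects, and "CHOP will recruit up to 40 subjects (approximately 20 male, 20 female), and MIR and MGH will each recruit a total of 16 subjects".

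Section 9 plans t-tests or ANOVA between age groups and "between different groups of categorical variables (sex, scanner manufacturer, field strength"). It then adds: "Multiple linear regression models will be utilized to evaluate the association between liver stiffness and the predictor variables adjusting for all other covariates". The covariates are not listed. Site appears in Section 9 only in connection with central image processing, and pulse sequence does not appear as a factor.

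**The concern.** Two separate problems sit behind the field-strength comparison, and a third behind the vendor comparison.

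- **Sequence.** If every 1.5T exam is GRE and every 3T exam is SE-EPI, field and sequence are one variable. No analysis can attribute a difference to either alone.
- **Site in the field test.** Most 3T subjects come from CHOP, which has no 1.5T scanner listed. MGH and MIR contribute only at 1.5T. A difference between CHOP and those two sites, in the children recruited or in local scanning, enters the pooled field difference.
- **Site in the vendor test.** Philips and CCHMC are the same group of subjects, so a CCHMC offset would be read as a Philips platform effect.

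Both aims hypothesise no difference. A site offset could produce an apparent difference or mask a real one. Either could lead users to split or pool normal values across scanners wrongly.

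**Working it through.** **Inputs.** Site totals are from Section 6, scanners from Section 4, and the SD of 0.3 kPa and 25% exclusion rate from the power calculation in Section 4. The documents do not give the split of CCHMC subjects by field or of CHOP subjects by vendor; equal splits are assumed, with CHOP at its maximum.

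**The plan's own figure.** The half-width at n=18 is t(0.975, 17) × 0.3/√18 = 0.149 kPa, which reproduces the stated 0.15. Also 18/0.75 = 24, and 32 + 40 + 16 + 16 = 104.

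**Layout.**

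| Vendor | 1.5T (generally GRE) | 3T (generally SE-EPI) |
|---|---|---|
| Philips | CCHMC 16 | CCHMC 16 |
| GE | MGH 16 | CHOP 20 |
| Siemens | MIR 16 | CHOP 20 |

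This gives 48 subjects at 1.5T and 56 at 3T. CHOP's share of 3T is 40/56 = 71%, or 32/48 = 67% if 3T enrolment stops at 24 per age group.

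**What can be estimated.** A model with an intercept, two vendor terms, field and three site terms has 7 columns but rank 6.

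- Field remains estimable, only from Philips 1.5T versus 3T within CCHMC.
- GE versus Siemens remains estimable, only from 3T within CHOP.
- Philips versus GE and Philips versus Siemens are not estimable.
- If sequence is added exactly as mapped, the rank stays at 6 and field is no longer estimable, even within CCHMC.
- A vendor-by-field interaction model also has rank 6, and still 6 with site columns added. Each cell comes from one site, so the interaction cannot remove site.

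**How much of a CHOP offset reaches the field coefficient.** With vendor in the model, the field coefficient is an average of the three within-vendor differences, weighted by n₁n₂/(n₁+n₂):

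- Philips: 16×16/32 = 8.00
- GE and Siemens: 16×20/36 = 8.89 each
- CHOP loading: (8.89 + 8.89)/(8.00 + 8.89 + 8.89) = 0.690

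Other splits give 0.667 (CHOP 16/16), 0.675 (CHOP 10/30) and 0.703 (CCHMC 12/20). MGH and MIR each load −0.345. Without vendor in the model the CHOP loading is 0.714, so adjusting for vendor barely helps.

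**Effect on the test.** After 25% exclusions the cells are 12, 12, 12, 12, 15 and 15 (36 versus 42). The standard error of the vendor-adjusted field coefficient is 0.3/√(6.00 + 6.67 + 6.67) = 0.068 kPa. The table gives the percentage of trials with p<0.05 when there is no field effect and only CHOP is shifted by an assumed amount:

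| CHOP offset (kPa) | Bias, 0.690 × offset | CHOP at 40 | CHOP at 32 |
|---|---|---|---|
| 0.03 | 0.021 | 6% | – |
| 0.05 | 0.034 | 8% | – |
| 0.10 | 0.069 | 17% | 15% |
| 0.15 | 0.103 | 32% | 28% |
| 0.20 | 0.138 | 50% | 45% |

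The bias column is for CHOP at 40; with CHOP at 32 the loading is 0.667. The within-CCHMC test stays at 5% throughout, because no CCHMC subject is shifted.

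**Precision of the contrasts free of site (95% half-widths).**

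- CCHMC 1.5T versus 3T, 12 versus 12: t(0.975, 22) × 0.3 × √(2/12) = 0.254 kPa
- CHOP GE versus Siemens, 15 versus 15: t(0.975, 28) × 0.3 × √(2/15) = 0.224 kPa
- Pooled field test, 36 versus 42: t(0.975, 76) × 0.3 × √(1/36 + 1/42) = 0.136 kPa

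**The case against.** The strongest reply is that the study aims at normal values across the range of MRI equipment, using each manufacturer's product sequence. On that reading, 1.5T product exam versus 3T product exam is the quantity wanted, and the sequence mapping is openly stated. This stands as far as it goes: it turns the sequence point into one of labelling. It does not touch the site component. The word for 'generally' in the plan also allows exceptions, so the aliasing with sequence is complete only if none occur; the plan names none.

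The size is also open to challenge, fairly. The offsets are assumed, small ones (0.03 to 0.05 kPa) do little harm, and CHOP may recruit fewer than 40. What enters the field coefficient is CHOP relative to the average of MGH and MIR, so an offset shared by all three cancels. A fixed 60 Hz frequency, common eligibility rules, one central reader, largely single-source hardware and sex balance all make large offsets less likely. They do not rule them out, because recruitment and scanning are local. Nor do the documents say that driver amplitude changes measured stiffness, so that difference is a further unseparated feature rather than a shown bias.

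Finally, the within-CCHMC contrast is weak. With 12 versus 12 it has about 22% power for a 0.15 kPa difference and 35% for 0.20 kPa; 80% power needs about 0.35 kPa. It also stays tied to sequence. That is correct, and is a reason to report its interval rather than its p-value. Using several sites was unavoidable given the scanners available, and no redesign is asked for.

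**Conclusion.** The concern holds. The aliasing follows from the scanner list and needs no assumed offset: Philips versus GE or Siemens cannot be told apart from CCHMC versus the other sites, and field strength cannot be told apart from sequence under the stated mapping. The pooled field coefficient also takes in about 69% of any CHOP offset (67–70% across the splits tried), with vendor adjustment making little difference. How often this would mislead depends on an offset that the documents do not give: from 8% of trials at 0.05 kPa to 50% at 0.20 kPa, against a nominal 5%, with SD 0.3 kPa, 25% exclusions, equal scanner splits and CHOP at 40. Section 9 does not list its regression covariates, so a model with vendor but without site is an assumption about what will be fitted; adding site would protect the field estimate but could not recover the Philips contrasts. Only secondary aims 1 and 2 are affected. The plan should be changed, but the primary age-group aim is not challenged.

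**What to change.** 1. Reword aim 2 as a comparison of the 1.5T product examination (generally 2D GRE) with the 3T product examination (generally 2D SE-EPI), and do not attribute the result to field strength alone.
2. Record the sequence actually used for each exam and report results by it.
3. Keep the planned regression and list its covariates: vendor, field/sequence, age group and sex. Beside it, report with 95% intervals the two contrasts that are free of site: Philips 1.5T versus 3T within CCHMC, and GE versus Siemens at 3T within CHOP. Do not rely on a vendor-by-field interaction to deal with site.
4. State that Philips versus the other vendors is a combined platform-and-site comparison, and limit aim 1's conclusion accordingly.

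The cost is wording, one recorded field and two contrasts from data already being collected; no scans or subjects are added. The price is narrower claims for secondary aims 1 and 2, and a site-free field interval nearly twice as wide as the pooled one (0.254/0.136 ≈ 1.9).

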There is one prior study of healthy pediatric patients that included 35 subjects (24 between ages 5-14 years and 11 between ages 15-18 years)[Etchell]. That study demonstrated that normal liver stiffness values were lower for healthy pediatric subjects than for healthy adult subjects (2.2 vs. 2.6 kPa). The authors also found a slight significant correlation between age and liver stiffness (r=0.38) but failed to demonstrate a difference in liver stiffness between subjects ≤14 years of age versus >14 years of age. While this prior study provides some information about normal liver stiffness in the pediatric population, it has key limitations. First, this study was performed with nonstandard multi-frequency MR elastography. One of the frequencies that was utilized (56 Hz) is close to the standard 60 Hz MR elastography utilized for clinical MRE, but differences in frequency utilized to measure tissue stiffness are known to influence liver stiffness measurements and thus normative data from this study may not apply to MR elastography performed with manufacturer standard technique. Second, the subjects imaged in this study were not fasting at the time of MR imaging. There are conflicting data regarding the effect of fasting (or lack thereof) on measured liver stiffness with some studies showing a stiffening effect of increased post-prandial splanchnic blood flow [Hines, Lemoine, Yin]. Third, while the subjects included in this study had no "known history of liver disease" MR fat fractions were not measured and serum liver function tests were not checked to confirm liver health. Finally, all examinations in this prior study were performed on a single manufacturer MR platform and at a single field strength, possibly limiting generalizability across other platforms.

MR elastography is a rapidly evolving technique and sequence improvements are constantly being developed. Additionally, new MRI techniques for assessment of diffuse liver disease are constantly being developed. At CCHMC only, additional imaging data will be acquired for exploratory aims related to these newer techniques.

4. STUDY DESIGN:

Study aims and hypotheses are as follows:

Primary aim/hypothesis – To determine normal liver stiffness values (and associated normal ranges) as measured by MR elastography for two pediatric age groups. We hypothesize that normal liver stiffness as measured by MR elastography will differ between the two pediatric age groups, increasing with increasing age.

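### Section 9 gives the age-group comparison to an unadjusted t-test or ANOVA, although recruitment is stratified by vendor and field strength; the adjusted regression already planned should decide it

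*Combined protocol and SAP*

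**What the plan says.** Section 4 (Study Design) hypothesises that stiffness differs between the two age groups and rises with age. For the primary aim it gives means, SDs and 95% confidence intervals per age group and adds that "values will be compared across groups". The power calculation in the same section says of the planned sample: "This sample size also provides 80% power to detect an effect size", namely d=0.67 between the age groups.

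Section 9 names the test: "Two sample t-test or one-way analysis of variance (ANOVA) will be used to assess for differences in liver stiffness between age groups". The same tests serve sex, manufacturer and field strength. Section 9 then plans correlations with continuous variables, which it does not name, and multiple linear regression on predictors and covariates, which it does not list. It does not link the regression to an aim, say whether age enters as the two groups or in years, or say which result decides the age hypothesis.

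The secondary aims in Section 4 build the scanner factors and sex into recruitment: "subject recruitment will be stratified across sites" (for vendor), "subject recruitment will be stratified across 1.5T and 3T magnets", and "approximately equal numbers of male and female subjects will be recruited in each of the two age groups". Section 6 repeats the sex balance within age group, vendor and field strength. The MR imaging text shows that the pulse sequence also changes with field strength: "generally 2D gradient recalled echo at 1.5T and 2D spin echo echo-planar imaging at 3T".

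**The concern.** The analysis named for the powered comparison does not use the structure built into recruitment. Children are spread over six vendor-by-field cells, and a t-test on the pooled data counts any difference between cells as noise. The planning SD of 0.3 kPa allows for no such noise, because it comes from a study of which Section 3 says that "all examinations in this prior study were performed on a single manufacturer MR platform and at a single field strength".

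The plan hypothesises no platform difference, but secondary aims 1 and 2 exist to check exactly that. The primary comparison should not depend on the answer. At stake are some power and a somewhat wider interval for the age difference. The plan also leaves it unclear which of two planned analyses a reader should treat as the answer.

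The wording that allows a t-test or an ANOVA is not itself a problem. With two age groups, one-way ANOVA and the pooled t-test are the same test.

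**Working it through.** **Inputs from the documents.** SD 0.3 kPa, n=18 per group, CI half-width 0.15 kPa, d=0.67, 80% power, 25% expected exclusions and about 24 recruited per age group per field strength (Section 4, power calculation); alpha 0.05 (Section 9); site totals 32+40+16+16=104 (Section 6); scanners by site (Section 4, research strategy).

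**Assumptions.** The documents give no platform effect. I take independent normal effects for the six vendor-by-field cells with SD τ = 0, 0.10 or 0.15 kPa, added to a within-platform SD of 0.3 kPa.

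**The plan's own figures.**
- CI half-width at n=18: t(0.975, 17)×0.3/√18 = 0.149 kPa, which matches 0.15.
- Power at d=0.67: with 36 evaluable per age group (18 at each of two field strengths), noncentrality is 0.67×√(36/2) = 2.84 on 70 df, which gives 80.05%. With 18 per age group it is 49.7%. The stated 80% therefore pools the two field strengths.
- Recruitment: 18/(1−0.25) = 24, matching the target.

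**Balanced cells by hand.** There are 72 children, 12 per cell, 6 from each age group. Cell effects cancel in the difference between age-group means, so its true standard error is 0.3×√(2/36) = 0.0707 kPa. The t-test instead estimates a variance of 0.3² + (12×5/70)τ²:
- τ=0.10: 0.09+0.0086 = 0.0986, SD 0.314
- τ=0.15: 0.09+0.0193 = 0.1093, SD 0.331

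The half-width is 1.994×SD×√(2/36), or 0.148 and 0.155 kPa. Adjusting for the six cells and sex leaves 64 df: 1.998×0.0707 = 0.141 kPa. The plan's difference is 0.67×0.3 = 0.201 kPa, and power is roughly Φ((0.201−half-width)/0.0707):
- unadjusted, τ=0.10: Φ(0.755) = 77.5%
- unadjusted, τ=0.15: Φ(0.645) = 74%
- adjusted: Φ(0.845) = 80%

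**Simulation** (20,000 runs for power, 40,000 for size; unadjusted / adjusted for the six cells and sex):

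| Setting | τ=0 | τ=0.10 | τ=0.15 |
|---|---|---|---|
| Power, 72 balanced | 80.5 / 80.5% | 77.7 / 80.2% | 73.7 / 79.9% |
| Size, 72 balanced | 5.1 / 5.0% | 4.2 / 5.1% | 3.3 / 5.1% |
| 95% CI half-width (kPa), 72 balanced | 0.140 / 0.141 | 0.147 / 0.141 | 0.155 / 0.141 |
| Power, 96 less a random 25% (72) | 79.6 / 78.6% | 76.9 / 78.6% | 73.4 / 78.9% |
| Power, 104 at site totals less a random 25% (78) | 83.0 / 82.2% | 80.5 / 82.3% | 76.6 / 81.8% |

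I re-ran these settings with separate code and 10,000 runs. The power figures agreed to within about half a point, for example 77.2 / 80.0% for balanced cells and 80.1 / 81.9% at the site totals, both at τ=0.10. In that re-run the site-total setting split the totals of CCHMC and CHOP equally between their two scanners, which is an assumption.

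With random exclusions and no platform effect, adjustment costs about 1 point. In the 96-less-25% setting it breaks even near τ=0.05 kPa (78.9 / 78.8%).

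**The case against.** The strongest reply has four parts.

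1. **An adjusted analysis is already planned.** This stands. A reader might infer that the plan ignores the scanner factors, but Section 9 has a multiple regression. What is missing is its role and the coding of age.

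2. **The primary aim is mainly estimation.** Section 2 states normal values and ranges as the primary purpose, and the sample size comes from interval width; the power is a by-product. This also stands and limits the weight of the point. But the hypothesis is a difference between age groups, and the plan powers it.

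3. **The t-test is valid.** A reader might infer inflated type I error. In every setting in the table, and under the planned balance generally, the test is unbiased and at or below about 5%. A rate of 8% to 11% can be produced, but only by assuming a 22-point difference between age groups in the share scanned at 3T together with a field effect of 0.2 to 0.3 kPa. Neither figure is in the documents. A rate of about 7.9% needs the t-test, the correlation and a regression on age in years all to be run, with any one allowed to decide. The plan states no such rule.

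4. **The loss is hypothetical and may be smaller.** Section 3 notes that most elastography hardware and software comes from one company, and Section 4 expects no vendor or field difference. A τ of 0.15 kPa implies an expected spread of about 2.53×0.15 = 0.38 kPa across six cells, close to the 0.4 kPa gap between children and adults cited in Section 3 (2.2 against 2.6). The 0.3 kPa SD may also be somewhat large within an age group, because the earlier sample covered ages 5 to 18 with r=0.38. Removing age entirely gives 0.3×√(1−0.38²) = 0.277, and about 0.281 within groups under an inferred age distribution. At 0.281 the unadjusted test has about 83% power at τ=0.10 and 78% at τ=0.15. All of this is fair. The adjusted test gains from the smaller SD too: 1.998×0.281×√(2/36) = 0.132, and Φ((0.201−0.132)/0.0662) is about 85%. The gap between the two tests therefore remains.

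**Conclusion.** The point holds in a limited form. Section 9 attaches the powered age comparison to a test that leaves out the recruitment factors, and it does not attach the planned regression to that comparison.

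With 36 evaluable per group and assumed platform SDs of 0.10 and 0.15 kPa, the cost is about 3 and 6 points of power, a test size of about 4% and 3.5%, and a half-width of 0.147 and 0.155 instead of 0.141 kPa. At the site totals less 25%, the unadjusted test keeps the planned 80% at 0.10 kPa and falls to about 77% at 0.15 kPa. If platforms do not differ there is nothing to gain, and uneven cells cost about 1 point.

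The documents do not support reading this as a biased primary test, an inflated error rate or an underpowered study. It is a cheap improvement of minor to moderate severity. Its size rests wholly on platform effects that the documents do not give.

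**What to change.** State in Section 9 that:

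- The age comparison is decided by the two-sided 0.05 test of the age-group coefficient in a linear model with vendor, field strength and sex, reported as an adjusted difference with its 95% confidence interval.
- Vendor and field strength preferably enter as the six vendor-by-field cells. Each cell belongs to one site in Section 4, so the cells also separate the four sites. The adjusted figures above are for this version; main effects alone would leave any vendor-by-field differences in the error term.
- Age is coded as the two groups in the deciding model. The unadjusted t-test, the correlation with age and the same model with age in years are supportive.
- Age-group means, SDs, confidence intervals and ranges are reported as planned.

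The cost is wording only: no new data and no more children. Five indicators for the cells and one for sex use 6 degrees of freedom. The price is about 1 point of power if platforms do not differ and exclusions leave the cells uneven.
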